#### Human Research Protections Program Investigator and Staff Training:

For this protocol, the following “just in time” human subjects protection training courses are required for investigators and staff:

- NIAID GCP course or CITI GCP modules
- Unanticipated Problems and Reporting Requirements in Biomedical Research

Total requested accrual

(0) Patients

(40) Healthy Volunteers

Project Uses Ionizing Radiation:  No  Yes (*attach RSC/RDRC documentation*)  
 Medically-indicated only  
 Research-related only  
 Both

IND/IDE  No  Yes (*attach FDA documentation*)  
Drug: C-T1650. Not yet submitted  
Sponsor: NIMH IRP

Drug: BPN14770: #127,905  
Sponsor: Tetra Discovery Partners, Grand Rapids, MI

Durable Power of Attorney  No  Yes

Multi-institutional Project  No  Yes

Institution#1 \_\_\_\_\_ FWA # \_\_\_\_\_  
Date of IRB approval \_\_\_\_\_ (*attach IRB documentation*)

Institution#2 \_\_\_\_\_ FWA # \_\_\_\_\_  
Date of IRB approval \_\_\_\_\_ (*attach IRB documentation*)

Data and Safety Monitoring Board  No  Yes

Technology Transfer Agreement  No  Yes  
Agreement type and number CTA Expiration Date 01/27/2028

Samples are being stored  No  Yes

Covered protocol requiring DEC approval  No  Yes

Flesch-Kincaid reading level of consent forms:

- Phase 1: 8.9
- Phase 2: 8.7
- Phase 3: 8.9
- Phase 4: 8.7

## **Précis:**

### **i. Objective**

Phosphodiesterase type 4 (PDE4) metabolizes 3',5'-cyclic adenosine monophosphate (cAMP), thereby terminating this second messenger. PDE4 is selective to cAMP over cyclic guanosine monophosphate. PDE4 has four isozymes—A, B, C, and D—and basic studies suggest that type D (PDE4D) may play a key role in cognitive function and depression. That is, PDE4D inhibitors are expected to improve cognitive function and depressive symptoms.

In collaboration with Tetra Discovery Partners, we have developed a PET ligand, C-T-1650, to selectively image PDE4D. This type D selective ligand was developed based on 3D structural differences between PDE4D and PDE4 type B (PDE4B). Our PET studies using C-T-1650 in nonhuman primate have shown promising results, and we now seek to evaluate it in healthy subjects.

This study has three primary objectives. First, we will determine whether the uptake of C-T-1650 in the brain reflects the distribution of PDE4D, as demonstrated by blocking with a PDE4D selective compound BPN14770, being developed by Tetra Discovery Partners for treating cognitive disorders including depression. Second, we will measure binding site occupancy of BPN14770 administered at doses that may be used in clinical trials. Third, we will measure the test/retest reproducibility of brain uptake quantified by kinetic modeling and using arterial blood samples.

### **ii. Study Population**

Healthy adult female and male volunteers (age ≥ 18) will have either brain (n = 30) or whole body imaging (n = 10).

### **iii. Design**

- a) Phase 1: We will begin with whole body scanning in a single human subject using up to 10 mCi C-T-1650. The aim of this first scan will be to detect a tracer that disproportionately accumulates in a single radiosensitive organ, such as the gonads. If we confirm that radioactivity is fairly widely distributed in the body, higher activities may be injected.
- b) Phase 2: Fifteen healthy subjects will have three brain PET scans using 20 mCi of C-T-1650. Scan 1 will serve as the baseline scan for comparison to enzyme occupancy studies (Scan 2 and 3). Scans 2 and 3 will be enzyme occupancy studies using the PDE4D selective medication BPN14770. Scans 2 and Scan 3 will be performed approximately 90-180 min after the first dose of BPN14770 and after three-day administration, respectively. Scan 3 will be performed approximately 90-180 min after the last dose of the three-day administration of BPN14770. The dose of BPN14770 is 50 mg BID for three days, and a single dose on the fourth day. Comparison between Scan 1 and 2 provides accurate measurement of nonspecific binding of C-T-1650. Comparison between Scan 1 and 3 provides enzyme occupancy at a stable plasma concentration of BPN14770 based on Phase 1/2 clinical trials performed by Tetra Discovery Partners. Blood samples will be measured for BPN14770 levels.

- c) Phase 3: To obtain dosimetry information, we will perform a whole body PET scan using  $^{11}\text{C-T-1650}$  (20 mCi) in up to nine healthy subjects.
- d) Phase 4: Fifteen healthy subjects will have two brain PET scans using 20 mCi of  $^{11}\text{C-T-1650}$  to study test/retest reproducibility of the PET measurement. BPN14770 will not be administered in Phases 1, 3 or 4.

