## **3. Subjects**

### **a. Description of study populations**

We propose to study four groups of participants:

Phase 1: One subject will have a whole body PET scan with 10 mCi of C-T-1650 to confirm that no organ has prominently high uptake of C-T-1650.

Phase 2: 15 healthy subjects will have three brain PET scans, baseline, about 90-180 min after the first dose of BPN14770 (Scan #2), and after three and a half-day administration of BPN14770 (Scan #3) to measure specific binding and *BPND* of C-T-1650 and binding site occupancy of BPN14770. The dose of BPN14770 is 50 mg BID (except for the last day in which subjects will take a single dose). BPN14770 levels will be measured in plasma samples.

Phase 3: Nine healthy subjects will have a whole body scan using 20 mCi C-T-1650 to estimate radiation-absorbed doses.

Phase 4: 15 healthy subjects will have two brain PET scans; test-retest kinetic brain imaging with arterial blood sampling.

Note: As described below in Section 10 (“Statistical Analysis”), these requested numbers account for and include subjects who may drop out.

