We propose to study up to 40 healthy volunteers: one in Phase 1 (whole body imaging with a low injection activity), 15 in Phase 2 (baseline and blocked brain scans), 9 (whole body imaging to estimate radiation-absorbed doses, and 15 in Phase 4 (test-retest kinetic brain imaging with arterial blood sampling).

To estimate the radiation exposure from this new radioligand, we will follow the prior suggestions from our laboratory [16], which have been approved by the NIH RSC. Specifically, we found that the average exposure of all published human studies with  $^{11}\text{C}$ -radioligands more accurately reflected the exposure to humans than estimation based on imaging in monkeys with that particular radioligand.

Phase 1: One subject will have a first-in-human whole body PET scan with 10 mCi  $^{11}\text{C}$ -T-1650 to confirm that no organ has prominently high uptake of  $^{11}\text{C}$ -T-1650.

Phase 2: 15 healthy subjects will have three brain PET scans, baseline (Scan #1), about 90-180 min after the first dose of BPN14770 (Scan #2), and after three and a half-day administration of BPN14770 (Scan #3). In each scan, 20 mCi of C-T-1650 will be injected. In Scan #1 and #2, the binding will be measured by kinetic brain imaging with arterial blood sampling. In addition, in all of Scan #1, 2, and 3, by using venous samples, radioligand binding will be measured as brain uptake (SUV) normalized to venous concentrations of C-T-1650 because an arterial line will not be placed in Scan #3 due to three-day interval between Scan #2 and 3. Venous samples will be analyzed for BPN14770 levels. The dose of BPN14770 will be 50 mg BID (except for the last day in which subjects will take a single dose).

Phase 3: Nine healthy subjects will have a whole-body scan using 20 mCi of C-T-1650 to estimate radiation-absorbed doses.

Phase 4: 15 healthy subjects will have two brain PET scans; test-retest kinetic brain imaging with arterial blood sampling.

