## **b. Radiation exposure risks**

Radiation exposure in this protocol will be from  $^{11}\text{C}$ -T-1650 and the associated transmission scans. To estimate the radiation exposure from this new radioligand, we will follow the suggestion from our laboratory [17] and approved by the NIH RSC and the FDA. Specifically, we found that the average exposure of all published human studies with  $^{11}\text{C}$ -radioligands more accurately reflected radiation exposure than estimation based on imaging in monkeys with that particular radioligand.

The average effective dose from 21 radioligands labeled with  $^{11}\text{C}$  was 0.019 rem/mCi [16]. Thus, the radiation exposure from a single injection of 20 mCi yields an effective dose of 0.38 rem, not including the transmission scan (described below), which is well below the NIH limit of 5 rem.

With regard to exposure from the transmission scan, the PET Department recently implemented [name] suggestion to decrease the current (amperage) and, thereby, the radiation from the CT. We do not need a high resolution (high current) image for attenuation correction; a low resolution, like that from a line source, is perfectly adequate to correct attenuation in the PET emission scan. With the lowered current, the exposure to the lens of the eye is now 0.26 rem, about 1/3 of the previous value.

We wish to maintain flexibility in the choice of PET cameras. Among the various PET cameras, PET/CT has the highest exposure. The effective doses for one head and one whole body transmission scan from a PET/CT are 0.02 and 0.66 rem, respectively. In addition, we allow for up to two transmission scans in case the subject temporarily leaves the camera (e.g., to urinate) or moves significantly.

The radiation exposure from the four phases of this protocol is as follows:

Phase 1: Whole Body Scan. The effective dose comes from 10 mCi radioligand (= 0.38 / 2 rem) plus two whole body transmission scans (2 \* 0.56 rem) for a total of 1.31 rem. This dose is described in the consent form as "about 2 rem."

Phase 2: Three brain scans. The effective dose comes from three injections of 20 mCi radioligand (3 \* 0.38 rem) plus up to six head transmission scans (6 \* 0.02 rem) for a total of 1.26 rem. This dose is described in the consent for as "about 1 rem."

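### The protocol specifies no dose calculation from the Phase 1 whole-body scan before Phase 2, and the dose totals described to participants do not follow one rounding rule

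*Combined protocol and SAP*

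**What the plan says.** **Sequence.** Précis iii (Design) states: "We will begin with whole body scanning in a single human subject using up to 10 mCi". Its aim is to find out whether the tracer concentrates in one radiation-sensitive organ; the gonads are the example given. The rule for going on is "If we confirm that radioactivity is fairly widely distributed in the body, higher activities may be injected". Section 3.a words the purpose as "to confirm that no organ has prominently high uptake", and Section 4.a repeats it. Neither wording carries a number. Phase 2 follows: "Fifteen healthy subjects will have three brain PET scans using 20 mCi of" the tracer. Section 4.d makes 20 mCi per injection a ceiling.

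**Dosimetry.** Précis iii and Sections 3.a and 4.a give the estimation of absorbed dose to Phase 3. Under Section 4.a, Phase 3 opens once three Phase 2 subjects have shown more than 40% specific binding. Yet Section 4.a also calls the whole-body work in Phases 1 and 3 dosimetry studies, and Section 10.b sizes the two together. Section 4.d describes one whole-body procedure for both phases: a transmission scan and serial emission scans from the head to below the gonads. Précis iv says whole-body organ uptake is quantified as SUV, but does not tie SUV to the Phase 1 decision.

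**Dose figures (Section 7.b).** The coefficient is introduced with "The average effective dose from 21 radioligands labeled with" carbon-11 and is 0.019 rem/mCi. Phase 1 is summed "for a total of 1.31 rem" and described to participants as about 2 rem. Phase 2 is summed "for a total of 1.26 rem" and described as about 1 rem. Phase 3 (1.5 rem) is described as about 2 rem and Phase 4 (0.84 rem) as about 1 rem.

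**The concern.** There are two linked points.

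First, the hazard that Phase 1 is meant to detect is a high dose to one organ. The reading that answers it has no threshold, no named organs and no dose. The only dose figure available before Phase 2 is an average effective dose over other tracers, which cannot show whether this tracer loads one organ. The scan that could give tracer-specific estimates is already planned, but the plan does not say that they are calculated before up to 15 healthy volunteers, who stand to gain no direct benefit, receive up to three 20 mCi injections each.

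Second, these volunteers decide on the basis of a rounded total. If totals that differ by 0.05 rem are described as about 1 and about 2 rem, the descriptions cannot be compared between phases. Phase 2 also shares its wording with Phase 4, although its total is half as large again.

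**Working it through.** **Inputs, all from Section 7.b unless noted:** 0.019 rem/mCi; 0.02 rem per head transmission scan; 0.66 rem per whole-body transmission scan as stated, 0.56 rem as used in the sums; up to two transmission scans per PET scan; limit 5 rem. Activities: 10 mCi (Phase 1), 3 × 20 mCi (Phase 2), 20 mCi (Phase 3), 2 × 20 mCi (Phase 4).

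**1. Reproducing the plan's totals.** Total = mCi × 0.019 + number of transmission scans × rem per scan.

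- Phase 1: 10 × 0.019 + 2 × 0.56 = 0.19 + 1.12 = 1.31 rem
- Phase 2: 60 × 0.019 + 6 × 0.02 = 1.14 + 0.12 = 1.26 rem
- Phase 3: 20 × 0.019 + 2 × 0.56 = 0.38 + 1.12 = 1.50 rem
- Phase 4: 40 × 0.019 + 4 × 0.02 = 0.76 + 0.08 = 0.84 rem

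All four agree with the text.

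**2. Is there one rounding rule?**

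| Phase | Total (rem) | Nearest rem | Rounded up | Described as | Total with 0.66 | Nearest rem |
|---|---|---|---|---|---|---|
| 1 | 1.31 | 1 | 2 | about 2 | 0.19 + 1.32 = 1.51 | 2 |
| 2 | 1.26 | 1 | 2 | about 1 | 1.26 | 1 |
| 3 | 1.50 | 2 | 2 | about 2 | 0.38 + 1.32 = 1.70 | 2 |
| 4 | 0.84 | 1 | 1 | about 1 | 0.84 | 1 |

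On the printed totals, nearest-rem rounding fails for Phase 1 and rounding up fails for Phase 2. With 0.66 rem per whole-body transmission scan, nearest-rem rounding gives all four descriptions. So either the wording is uneven or the Phase 1 and Phase 3 totals rest on the wrong one of two values. The documents do not say which.

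**3. Size of the Phase 2 rounding.** (1.26 − 1) / 1.26 = 21% below the computed total. Phase 2 against Phase 4: 1.26 / 0.84 = 1.5.

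**4. How far the Phase 2 total depends on the class average.** The documents give no coefficient for this tracer, so assume that it is m × 0.019. The total is then 1.14m + 0.12:

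- m = 0.5: 0.69 rem
- m = 1: 1.26 rem
- m = 2: 2.40 rem
- m = 3: 3.54 rem

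The total reaches 1.5 rem, where nearest-rem rounding no longer gives 1, at (1.5 − 0.12) / 60 = 0.023 rem/mCi, or m = 1.21. It reaches 5 rem at (5 − 0.12) / 60 = 0.0813 rem/mCi, or m = 4.28. At m = 1 it is 1.26 / 5 = 25% of the limit. Section 7.b makes the 5 rem comparison only for one injection (0.38 rem), not for the Phase 2 total.

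None of this bears on organ dose, which cannot be calculated from the documents.

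**5. Lens.** Section 7.b gives 0.26 rem to the lens from CT, without saying whether this is per scan, and does not sum it. If it is per scan, Phase 2's maximum of six head scans gives 6 × 0.26 = 1.56 rem. No lens limit is given for comparison.

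**The case against.** The order is deliberate and argued for. Section 4.a says that requiring dosimetry in several subjects first exposed people needlessly when a tracer then failed in the brain. It adds that the Radiation Safety Committee therefore allowed brain imaging after one whole-body scan, and that another protocol followed the same steps. Sections 4.a and 7.b explain the class average: it was found more accurate than extrapolation from monkey imaging, and Section 7.b reports that the committee and the FDA accepted this approach. The Phase 1 scan is itself a look at organs, with SUV available. One subject gives a rough estimate and covers one sex's gonads, so it is no substitute for an average over 21 tracers. Describing 1.26 rem as about 1 is ordinary rounding.

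All of that stands. It justifies the order and the use of the average. It does not explain why the dose that a planned scan can yield has no stated place before Phase 2, nor does it remove the conflict between 0.66 and 0.56.

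A reader might infer that Phase 2 exposes people beyond an accepted limit. The figures do not support this. A reader might also infer that organ doses will not be calculated before Phase 2. The documents are silent on the timing, which is less than ruling it out. Nor do they support the view that Phase 2 participants are singled out for an understated figure: on nearest-rem rounding the outlier is Phase 1, and the two transmission values may explain it.

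**Conclusion.** The point holds as a gap in specification and an inconsistency in disclosure, not as evidence of unsafe exposure.

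- **Gap:** up to 60 mCi per person follows a reading with no numerical criterion. The only prior dose figure is a class average that cannot speak to a single organ.
- **Inconsistency:** totals 0.05 rem apart are described as about 1 and about 2 rem, and 0.66 against 0.56 rem moves Phases 1 and 3 by 0.20 rem each (to 1.51 and 1.70). Phase 2's own total is unaffected, and its description is 21% below it.

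This rests on three assumptions: that silence on the timing of Phase 1 dose estimates means no step is specified; that the consent forms, which were not available for review, read as Section 7.b reports; and that 20 mCi per injection and two transmission scans per PET scan are ceilings, so that the Phase 2 sum is a planned maximum for a tracer at the class average.

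**What to change.** Keep the sequence and the class average. No activity limit or escalation rule is proposed here.

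1. In Sections 4.a and 7.b, state that organ and effective dose estimates from the Phase 1 scan will be calculated and documented before Phase 2 and reported beside the class-average totals, noting that they come from one subject of one sex.
2. In Section 7.b, reconcile 0.66 and 0.56 rem per whole-body transmission scan and recompute the Phase 1 and Phase 3 totals if needed.
3. Give every phase's total in the consent forms to the same precision; at one decimal, Phase 2 reads about 1.3 rem and Phase 4 about 0.8 rem.
4. Say whether the 0.26 rem lens figure is per scan and, if so, give the sum for each brain-imaging phase.

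The cost is a few days of analysis on a scan already planned, an edit to Section 7.b, revised consent wording and a slightly less favourable Phase 2 figure. The risk is that a one-subject estimate is read as more precise than it is; reporting it beside the class average limits that.

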**iv. Outcome Measures**

For whole body imaging, organ uptake will be quantified as a Standardized Uptake Value (SUV), which normalizes for injected activity and body weight. For Scan 1 and 2 of Phase 2 and all scans of Phase 4, uptake will be quantified as total distribution volume ( $V_T$ ) calculated with kinetic modeling and serial concentrations of parent radioligand in arterial plasma. For Scan 3 of Phase 3, brain uptake (SUV) normalized to plasma concentrations of  $^{11}\text{C-T-1650}$  will be used to measure radioligand binding because the interval between Scan 2 and 3 is too short to repeat placing arterial line. From  $V_T$  or normalized SUV, occupancy of BPN14770 and nonspecific binding of  $^{11}\text{C-T-1650}$  will be measured. Occupancy of PDE4D will be compared to blood levels of BPN14770.

## List of Abbreviations

AUC	area under the curve
BID	twice a day
$BP_{ND}$	Binding potential relative to nondisplaceable distribution volume, specific-to-nondisplaceable ratio of distribution volume
cAMP	3',5'-cyclic adenosine monophosphate
MRI	magnetic resonance imaging
PDE4	phosphodiesterase type 4
PDE4D	PDE4 subtype D

PET	positron emission tomography
SUV	standardized uptake value
$BP_{ND}$	specific-to-nondisplaceable ratio of distribution volume
$V_T$	total (specific plus nondisplaceable) distribution volume

## 1. Introduction and Background

### **PDE4D inhibitors produce cognitive improvement and may show antidepressant effects**

PDE4 terminates signal transduction of G-protein-coupled receptors by metabolizing the second messenger cAMP. Because of the prevalence of G-protein-coupled receptors, PDE4 plays critical roles in a number of brain disorders including Alzheimer's disease and major depressive disorder.

A large number of pre-clinical and clinical trials have been performed using PDE4 inhibitors. Uncontrolled clinical studies conducted in the late 1980s and early 1990s with rolipram, an isozyme nonselective PDE4 inhibitor, found that this agent had antidepressant effects; however, the ratio of efficacy to adverse reactions limited its clinical use [1]. Two possible causes have been hypothesized for the low ratio of efficacy to adverse reaction: little selectivity of rolipram among the four PDE4 isozymes [2] and high inhibition of PDE4 activity because rolipram is a competitive inhibitor [3]. Building on these hypotheses, PDE4D selective negative allosteric modulators have been developed which induced cognitive improvement without causing emesis [3]. Inhibition of PDE4D is also expected to show antidepressant effects because PDE4D KO mouse showed antidepressant-like effect on behavior [4]

As described in the following subsections in detail, we have performed extensive studies using  $^{11}\text{C}$ -(R)-rolipram, which binds to all four PDE4 isozymes. To further investigate the role of PDE4 in brain disorders, a PET ligand that binds selectively to one of the four PDE4 isozymes is needed. Tetra Discovery Partners has developed a new PDE4D selective ligand,  $^{11}\text{C}$ -T-1650. We tested  $^{11}\text{C}$ -T-1650 in monkey PET studies and confirmed that specific binding of  $^{11}\text{C}$ -T-1650 is greater than that of  $^{11}\text{C}$ -(R)-rolipram, although T-1650 binds to only one subtype of PDE4 while rolipram binds to all subtypes. This specific binding suggests that  $^{11}\text{C}$ -T-1650 has much higher in vivo affinity than  $^{11}\text{C}$ -(R)-rolipram for PDE4.

We will also measure the enzyme occupancy by doses of BPN14770 that might be used in clinical studies and relate this to plasma levels of the drug. If all studies proceed well, the results will be used to guide a therapeutic trial in major depressive disorder (MDD) to improve cognitive function and depressive symptoms.

### **Previous PET studies using $^{11}\text{C}$ -(R)-rolipram, a PDE4 isozyme nonselective inhibitor *PET imaging of the cAMP cascade***

PET imaging of PDE4 with  $^{11}\text{C}$ -(R)-rolipram has been successfully used to study cAMP cascade activity *in vivo*. PDEs hydrolyze the second messengers cAMP and cyclic guanosine monophosphate (cGMP) to terminate signal transduction. Eleven PDEs exist in the human body. PDE4 is selective to cAMP and is present in both brain and peripheral organs such as heart, lungs, kidney [5], immune cells [6], osteoclasts [7], and osteoblasts [8]. Rolipram is a selective PDE4 inhibitor; PDE4 has four isozymes, and rolipram is not selective among these isozymes.

[figure not shown]
Our studies—described below—demonstrated that  $^{11}\text{C}$ -(R)-rolipram PET is a valuable method for detecting cAMP cascade activity in living human and animal subjects. Because PDE4 is present in almost all brain regions and no regions without PDE4 are available to use as a reference to measure rolipram binding, we used  $^{11}\text{C}$ -(R)-rolipram concentrations in arterial plasma (i.e., metabolite-corrected arterial input function) to measure rolipram binding in the brain [9, 10]. We also showed that rolipram binding can be accurately measured using only four arterial samples [9].

Broadly, the cAMP theory of depression posits that depression is caused by low cAMP signaling. The corresponding theory regarding the relevant mechanism of treatment is that chronic, but not acute, administration of antidepressants upregulates cAMP signaling. Although the cAMP theory of depression has limited supporting data, evidence for the mechanism of antidepressants has repeatedly been confirmed in animal studies. Chronic, but not acute, administration of all classes of antidepressants, as well as electroconvulsive therapy, upregulates several components of the cAMP pathway, including PDE4.

PDE4, an important component of the cAMP cascade, selectively metabolizes cAMP in the brain to the inactive monophosphate. Rolipram is a reversible inhibitor of PDE4, and binding of  $^{11}\text{C}$ -(R)-rolipram provides a measure of the activity of this enzyme in the brain. Due to a feedback mechanism, *in vivo* binding of  $^{11}\text{C}$ -(R)-rolipram reflects the activity of the cAMP cascade; essentially, increased cAMP stimulates protein kinase A (PKA), which phosphorylates PDE4 that, in turn, increases rolipram binding.

[figure not shown]
